Hypothesis I-a: tDCS will be safe in AIS patients with no increased risk of symptomatic intracranial hemorrhage (SICH) within the 24-hour period after stimulation. Hypothesis I-b: tDCS will not increase the rates of asymptomatic intracranial hemorrhage, early neurological deterioration (NIHSS during the 24-hour period after stimulation), 90-day mortality, and all serious adverse events. Hypothesis I-c: Majority of AIS patients ($\geq 90\%$) will tolerate the tDCS by completing at least 75% of the stimulation period with no major stimulation related pain, discomfort and skin changes.

Specific Aim II: To determine the feasibility of delivering tDCS in AIS.

Hypothesis II-a: tDCS will be started more rapidly over the course of the study and in the last 10 patients median time from randomization to tDCS initiation will be ≤ 10 minutes.

Specific Aim III: To explore the potential imaging and clinical efficacy of tDCS in AIS.

This aim will be accomplished by measuring, in actively treated and sham patients:

- 1) Early and late penumbral salvage, defined as proportion of penumbral tissue on baseline multimodal MRI that does not proceed to infarct on 2-hour and 24-hour MRI (PWI);
- 2) Early and

late collateral enhancement, evidenced by reduced perfusion lesion volume on 2-hour and 24-hour perfusion-weighted MRI (PWI); **3)** Early and late reduction in infarct growth from baseline to 2-hour and 24-hour MRI; **4)** Early improvement in neurologic deficit (NIHSS at 24h); **5)** Improvement in final 3-month disability and quality of life (modified Rankin scale, AMC Linear Disability Scale, EQ-5D, and Barthel Index)

Impact

This in-hospital safety trial, in non-thrombectomy candidates in a closely-observed, Emergency Department and hospital settings, will identify tDCS dose regimens that are feasible, well-tolerated, and preliminarily safe in patients with acute ischemic stroke. Study finding will identify the most promising dose regimens to advance to phase 2b and pivotal phase 3 efficacy trials for two patient populations with pressing need for improved therapies: 1) thrombectomy ineligible patients (standalone neuroprotection), and 2) thrombectomy-eligible patients (bridging neuroprotection in prehospital and early ED-arriving patients).

B. Background and Significance

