This proposal is a prospective, single-center, dose-escalation safety, tolerability and feasibility study of tDCS in acute stroke patients with substantial salvageable penumbra due to a large or medium vessel occlusion who are ineligible for endovascular therapy. The primary safety endpoints will be symptomatic intracranial hemorrhage during the 24-hour period after stimulation. Secondary measures of safety will include asymptomatic intracranial hemorrhage, early neurological deterioration, 3-month mortality and all

serious adverse events. Tolerability will be judged based on the percentage of the patients completing the protocol-assigned stimulation treatment and secondarily, the rate and severity of cutaneous, neurologic, nociceptive or other adverse effects will be assessed. Feasibility endpoints will analyze the speed with which tDCS will be implemented. Finally, we will explore signals of potential efficacy by examining the imaging biomarkers, including penumbral salvage, collateral enhancement, and infarct growth, and clinical outcomes of early neurologic deficit evolution, and 3-month global disability and health-related quality of life.

D2. Technology

D.2.1. tDCS Device and Stimulation Parameters

The study will employ a Soterix™ high-definition DC-Stimulator, owned by the principal investigator. This tDCS unit consists of a stimulator, 4x1 HD interface and an adjustable cap with pre-maid openings that quickly and easily fits different head sizes. (Figure 5). The cap will be loaded with plastic electrode holders. These will be filled with conductance gel (Signa® gel), 1 cm² electrodes will be placed in the holders, and the holder then locked.

[figure not shown]

Figure 5. Shows an example of electrode positioning in a 4 to 1-ring configuration in a patient with left M1 occlusion. A) The reference electrodes (anode-blue) are positioned on F3, T3, Cz and P3 and the center electrode (cathode-red) is positioned over the C3 (central sulcus). B) shows the computational modeling of the electrical field, concentrated over the MCA territory. C) Shows the electrode positioning on the tDCS HD cap, the schematic of the tDCS stimulator connected to the HD interface, and the Soterix™ HD tDCS unit (stimulator + interface) that will be used in this study. This stimulator connects to the adjustable cap. D) Shows the penumbral region on the perfusion MRI of the patient with L MCA occlusion.

D.2.2. Montage

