We will implement a traditional 3+3 (rule-based, modified Fibonacci) dose escalation design, with 3:1 randomization to active treatment vs sham control. There will be 6 dose tiers, reflecting increasing intensity and duration of stimulation: Tier 1 – 1 mA, single 20 - min cycle; Tier 2– 2 mA, single 20 min cycle; Tier 3 – 1 mA, 2 cycles of 20 min/20 min off; Tier 4– 2 mA, 2 cycles of 20 min/20 min off; Tier 5 – 1 mA, 3 cycles of 20 min/20 min off; Tier 6 – 2 mA, 3 cycles of 20 min/20 min off (Figure 7). Patients in the sham stimulation arm at all the tiers will have the cap and electrodes in place, and switches moved but without any delivered electrical stimulation. While the highest dose tier in this study is expected to be fully safe, based on preclinical and clinical studies^{12,19}, since this is a first-in-human study in acute stroke, a formal escalation to higher dose tiers is prudent.

Figure 7. This figure shows the 6 escalating tiers. Blue represents 1 mA and purple shows 2 mA of tDCS. Symptomatic ICH (SICH) in none of the three patients in a tier will result in escalation. However, SICH in one patient, 3 more patients and 1 sham will be enrolled at the same tier.

D.4. Management during and post stimulation period

Figure7: Technician-filled tolerability form	Presence		Severity		Effect on the study treatment (Shortened the stim duration)		Duration/Frequency			Treatment			
	A	P	M	Mod	S	Y	N	< 50 % of stim period	≥50% of stim period	lasted after stim period (min)	None	Con	Med
Adverse Events													
Rash													
Skin dryness													
Hair loss													
Itching													
Hives													
Skin Sensitivity to light													
Skin soreness													
Skin redness													
Skin darkening													
Numbness													
Tingling													
Dizziness													
General Pain													
Headache													

*A=Absent, Con=Conservative therapy such as cold pack and lotion, M= Mild, Mod=Moderate, Med=Medication such as topical steroid, N= No, P= Present, R: Resolved, S: Severe, Stim= Stimulation, Y=Yes.

Figure 8. Shows the technician-filled tolerability form. The selected items are based on the most common reported adverse effects associated with tDCS.

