For the final statistical analysis of the primary SICH safety endpoint, a chi-square test will be used to detect differences in the rate of SICH between the active treatment and sham patients and higher and lower dose tiers. The treatment will be considered to have exhibited adequate safety in the current trial to proceed to future, larger, pivotal efficacy trials if tDCS results in lower or equivalent rates of SICH compared to sham.

E.2.3.3. Secondary Safety Endpoints Analysis

In secondary safety endpoint analyses, the following will be compared between the active treatment and sham patients, and between higher and lower dose tiers, using chi-squared tests: **1) Asymptomatic ICH by 24h** (intracranial hemorrhage not associated with NIHSS worsening ≥ 4); **2) Early neurologic deterioration** (worsening ≥ 4 on NIHSS during the 24-hour period after stimulation, with or without intracranial hemorrhage); **3) All-cause mortality at day 90 (mRS);** and **4) All serious adverse events.**

E.3.3. Tolerability Endpoint Analysis

The lead tolerability endpoint is completion of the protocol-assigned stimulation treatment without early cessation due to cutaneous, neurologic, nociceptive or other adverse effects. Experience with tDCS in post-stroke patients indicates only infrequent cutaneous (itching, tingling) adverse effects are likely to occur. Accordingly, for the current study, a patient will be considered to have tolerated the procedure if at least 75% of the stimulus period was completed. The treatment will be considered generally tolerable if, among all enrolled patients, tolerated procedures are achieved in $\geq 90\%$ of patients, assessed with a one-sided p value of 0.025. Secondary tolerability endpoints will be the

rate and severity of cutaneous, neurological, and pain items of the technician-filled (Figure 7) and patient-filled tolerability forms ⁴⁹, descriptively compared between active treatment and sham patients, and between higher and lower dose tiers.

E.3.4. Feasibility Endpoint Analysis (Specific Aim 2)

A time-motion analysis and mock run-throughs will be conducted prior to first enrollment. Nonetheless, it is anticipated that processes to optimize rapid placement of the cap and electrodes will continue to improve with experience gained from initially enrolled patients. The predefined success threshold for feasibility will be median time from randomization to tDCS initiation \leq 10 minutes in the last 10 enrolled patients.

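### The per-patient tolerability rule in E.3.3 omits Hypothesis I-c's condition of no major pain, discomfort or skin change, and conflicts with the section's own lead endpoint

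*Combined protocol and SAP*

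**What the plan says.** Tolerability is described in four places.

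- **Specific aims, Hypothesis I-c.** At least 90% of patients are expected to tolerate tDCS by "completing at least 75% of the stimulation period with no major stimulation related pain, discomfort and skin changes".
- **Design overview, just before D2.** "Tolerability will be judged based on the percentage of the patients completing the protocol-assigned stimulation treatment and secondarily, the rate and severity of cutaneous" and related effects.
- **E.3.3, lead endpoint.** This is "completion of the protocol-assigned stimulation treatment without early cessation due to cutaneous, neurologic, nociceptive or other adverse effects".
- **E.3.3, per-patient rule.** A few lines later, "a patient will be considered to have tolerated the procedure if at least 75% of the stimulus period was completed". The group criterion is then at least 90% of all enrolled patients, with a one-sided p value of 0.025.

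Symptoms enter E.3.3 only as secondary endpoints: the "rate and severity of cutaneous, neurological, and pain items of the technician-filled (Figure 7) and patient-filled tolerability forms" are compared descriptively between active and sham and between higher and lower tiers.

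Section D.4 (Dose Tiers and Randomization) gives tiers 1-2 a single 20-minute cycle, tiers 3-4 "2 cycles of 20 min/20 min off" and tiers 5-6 "3 cycles of 20 min/20 min off". E.3.3 does not say whether the stimulus period means minutes with current on or elapsed minutes. The term major in I-c is not defined.

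**The concern.** Aim I is to establish tolerability, and the Impact paragraph says the trial will identify regimens that are well tolerated. The rule deciding who counts should therefore be the one the hypothesis states.

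The E.3.3 rule contains only the completion half of I-c. A patient can have a severe burn-like skin reaction or severe pain and still be scored as a success, provided 75% was delivered. A patient who stops because of an adverse effect at any point from 75% up to full completion is also a success, although the lead endpoint in the same section would make that patient a failure.

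At stake is the meaning of the headline tolerability rate. If the wordings stay unreconciled, the choice between them could also be made after the results have been seen.

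**Working it through.** **Inputs.** The three per-patient wordings come from Hypothesis I-c and E.3.3. Cycle numbers and lengths come from D.4. The sample size of 24 to 48 comes from E.2.1 and reproduces: 6 tiers × (3 + 1) = 24, and 6 × 2 × (3 + 1) = 48. It is used here only as a denominator, since the plan gives no calculation for tolerability.

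**Step 1. Apply the wordings to the same patients** (a tier with 60 minutes of current; severe is taken as major, which is my assumption).

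| Patient | Lead endpoint, E.3.3 | Hypothesis I-c | 75% rule, E.3.3 |
|---|---|---|---|
| Completes 60 of 60 min, severe skin reaction | met | not met | met |
| Stops at 46 of 60 min (76.7%) for severe pain | not met | not met | met |
| Stops at 46 of 60 min for a minor symptom | not met | met | met |

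The first two rows show the gap against I-c. The last two show the gap against the lead endpoint. The third row shows that I-c and the lead endpoint also disagree with each other, so adopting I-c alone does not settle every case.

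**Step 2. What 75% requires, on current-on time.**

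- Tiers 1-2: 0.75 × 20 = 15 min.
- Tiers 3-4: 0.75 × 40 = 30 min, which is cycle 1 plus 10 of the 20 min of cycle 2.
- Tiers 5-6: 0.75 × 60 = 45 min, which is cycles 1 and 2 plus 5 of the 20 min of cycle 3. Up to 15 min of cycle 3 may be missed.
- Two full cycles alone in tiers 5-6: 40/60 = 66.7%, which does not meet the cut.

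**Step 3. Effect on the rate.** One reclassified patient changes it by 1/24 = 4.2 percentage points, or 1/48 = 2.1. As an illustration (assumed, not predicted), let 3 of 24 patients stop for adverse effects between 75% and full completion while the rest complete. The 75% rule gives 24/24 = 100%; the lead endpoint gives 21/24 = 87.5%, below 90%.

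**The case against.** The best defence is that the 75% sentence is a deliberate operational form of the lead endpoint. E.3.3 presents it as following from the expectation that only infrequent skin effects will occur, and the design overview uses the same order, completion first and symptoms second. This stands in part: the main conflict is between I-c and E.3.3. But that expectation does not explain why a condition written into the hypothesis is absent from its analysis.

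It is also true that symptom severity is recorded and reported, and that the DSMB reviews all safety data at each tier. Nothing is lost to safety oversight. What is lost is the symptom condition in the prespecified tolerability verdict. Nor is the 75% cut peculiar to E.3.3: I-c uses it too, and any proportional cut lets the end of the last cycle be missed.

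Three stronger readings may tempt a reader and are not supported.

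- *That tiers 5-6 can count as tolerated with none of cycle 3 delivered.* This needs off-time to count. On 100 elapsed minutes, 75% is 75 min, inside the 60-80 min off interval; with a trailing off interval (120 min) it is 90 min, or 10 min into cycle 3. The footnote to the schedule in D.6.1 and the management section after D.4 use stimulation period and cycle for the current-on intervals, which gives 5 min of cycle 3.
- *That the rule can declare the three-cycle tiers tolerable.* E.3.3 gives one verdict over all enrolled patients and none by tier.
- *That a patient stopped by a device fault meets the lead endpoint.* That patient did not complete the assigned treatment.

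**Conclusion.** The point holds as an inconsistency that should be corrected. The lead tolerability criterion, followed as written, does not test Hypothesis I-c, and it scores as successes some patients whom the lead endpoint sentence would score as failures.

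Its size in patients cannot be derived from the documents. It depends on how many have a major symptom, or stop for an adverse effect, after reaching 75%; E.3.3 expects such effects to be infrequent.

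A reader might infer that the verdict flips on one patient around 90%, with 22 of 24 or 44 of 48 as passing counts. The documents do not support that, because the same sentence attaches a one-sided 0.025 without naming a null value. If the null is 90%, even 24/24 gives p = 0.9^24 = 0.080, and at 48 patients only 48/48 succeeds (p = 0.0064; 47/48 gives 0.040). The illustration in the working therefore changes the verdict only if 90% is read as a point estimate. The form of that test is a separate matter.

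The conclusion assumes that a severe skin or pain event would be major. The 45-minute figure assumes current-on time.

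**What to change.** Use one per-patient definition in E.3.3 and repeat it in Hypothesis I-c and the design overview:

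- **Tolerated** means at least 75% of assigned current-on time delivered and no major stimulation-related pain, discomfort or skin item.
- **Major** is defined in advance. Rated severe on the technician form is one candidate; it is a choice for the sponsor to confirm, as the form shown has no item named discomfort.
- **Stops for an adverse effect after 75%.** State whether they are failures, as the lead endpoint implies, or allowed when the symptom is not major, as I-c implies. Align the lead endpoint sentence with the answer.
- **Stops for other reasons.** State how they count.
- **Stimulus period** is defined as current-on time.
- **Descriptive supplement.** Report by tier the proportion completing every assigned cycle.

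Settle this before tolerability results are examined. No dose, schedule or escalation rule changes. The technician form already records severity and whether a symptom shortened stimulation, but shows no field for minutes delivered or for other reasons for stopping; both must be added. The tolerability rate may come out slightly lower than under the 75% rule alone.

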The trial will be monitored by an Independent Data and Safety Monitoring Board (DSMB). [name] from department of neurorehabilitation will lead the DSMB. DSMB will assess for the causal relationship of the serious adverse event to the study treatment as definite, probable, possible, unlikely, or unrelated.

DSMB will meet at the completion of each dose tier, review all safety data, and determine whether the study will proceed to the next dose tier. DSMB deliberations will be guided by: 1) a formal stopping/escalation rule, based on the occurrence of the lead safety endpoint, symptomatic intracranial hemorrhage (SICH), and 2) The DSMB members' clinical judgement upon review of all other safety outcomes. In addition, DSMB will monitor separately the patients who enroll in the study with a stroke scale 0-3 during the study as they are treated to determine if they have an increase in NIHSS of 2 or more or which is disabling.

Furthermore, Food and Drug Administration (FDA) will be notified if there is one occurrence of SICH prior to repeating the tier or escalating to a higher tier.

E. 2. Statistical Design and Analyses Plan

E.2.1. Sample size

The study sample size derives from the use of the 3+3, rule-based, modified Fibonacci, dose escalation design, with 3:1 randomization to active treatment vs sham control. There will be 6 dose tiers, reflecting increasing intensity and duration of stimulation (Figure 7). The 3+3 study design (3 patients and 1 sham) with 6 dose tiers yields a sample size of at least 24 and potentially up to 48. The 3+3 design is the classical approach to dose escalation in first-in-human studies.^{57,58} While newer, adaptive designs for dose escalation trials have been developed, they are more complex and have limited advantages when major toxicities are not expected.⁵⁹ Therefore, the rule-based, 3+3 design remains the dominantly employed approach in current dose-escalation studies. We will take every step to avoid missing data by scheduling of the follow-up visits early in visit time windows and readiness to travel to the patient's location to perform needed assessments. Should any missing data occur, primary analyses will be performed using multiple imputation, with sensitivity analyses including complete case and worst possible outcome analyses.⁶⁰

E.2.2. Baseline characteristics

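### The lead tolerability rule gives one verdict for six tiers and sham together, so it cannot show which regimens are well tolerated

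*Combined protocol and SAP*

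**What the plan says.** Under E.3.3, "a patient will be considered to have tolerated the procedure if at least 75% of the stimulus period was completed". The overall criterion follows: "The treatment will be considered generally tolerable if, among all enrolled patients, tolerated procedures are achieved in" at least 90% of patients, with a one-sided p value of 0.025. The plan names neither the null hypothesis nor the test.

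The tiers in D.4 (Dose Tiers and Randomization) run from one 20-minute cycle at 1 mA to "Tier 6 – 2 mA, 3 cycles of 20 min/20 min off". Sham patients wear the cap and electrodes but receive no current. In E.2.1 each of the six tiers takes three active patients and one sham patient, and the plan states that this "yields a sample size of at least 24 and potentially up to 48". Allocation is by "3:1 randomization to active treatment vs sham control".

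The Impact paragraph of section A says the trial "will identify tDCS dose regimens that are feasible, well-tolerated, and preliminarily safe in patients with acute ischemic stroke".

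The plan looks at dose in other places. E.2.3.1 has a tier-by-tier escalation rule based on symptomatic intracranial hemorrhage (SICH). E.2.3.2 and E.2.3.3 compare safety endpoints between higher and lower tiers. E.3.3 does the same, descriptively, for the rate and severity of symptoms on the tolerability forms. Completion of stimulation, the lead tolerability endpoint, has no by-dose result.

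**The concern.** If intolerance occurs, it is most likely in the longer and stronger tiers, while most of the denominator comes from shorter or weaker tiers and from sham. A pooled proportion can therefore hide poor completion in one tier. It can also, under a strict reading, withhold the claim from every tier because of one patient in one tier. In both cases the reader learns something about the treatment in general and nothing about a particular regimen, which is what the Impact paragraph promises. Because the null hypothesis is unstated, it is also unclear which of these two errors the rule is exposed to.

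**Working it through.** **Inputs.** Six tiers, each with 3 active + 1 sham, doubled if expanded (E.2.1, E.2.3.1); threshold 90% and one-sided 0.025 (E.3.3). I assume all six tiers are opened.

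**The plan's own figure.** 6 × (3 + 1) = 24 and 6 × 2 × (3 + 1) = 48, as stated. Active patients number 18 to 36 and sham 6 to 12.

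**Reading A: observed proportion at least 90%.**
- 24 enrolled: 0.9 × 24 = 21.6, so 22 are needed and 2 may fail. Both may be in tier 6: 2 of 3 failing gives 22/24 = 91.7%, a pass; 3 of 3 gives 21/24 = 87.5%, a fail.
- 48 enrolled: 0.9 × 48 = 43.2, so 44 are needed and 4 may fail: 4 of 6 in tier 6 gives 44/48 = 91.7%, a pass.

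**Reading A, active patients only.**

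| Active patients | Tier-6 failures | Rate | Result |
|---|---|---|---|
| 18 | 1 of 3 | 17/18 = 94.4% | pass |
| 18 | 2 of 3 | 16/18 = 88.9% | fail |
| 21 (one other tier expanded) | 2 of 3 | 19/21 = 90.5% | pass |
| 36 | 3 of 6 | 33/36 = 91.7% | pass |
| 36 | 4 of 6 | 32/36 = 88.9% | fail |

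**How often reading A passes with 24 enrolled.** Assume sham always completes. With F the number of failures, the pass probability is P(F in 15 active patients of tiers 1–5 + F in 3 of tier 6 ≤ 2). Suppose tolerability is 98% in tiers 1–5 and 50% in tier 6. The chances of 0, 1 and 2 failures in tiers 1–5 are 0.7386, 0.2261 and 0.0323, so the sum is 0.7386 × 7/8 + 0.2261 × 4/8 + 0.0323 × 1/8 = 0.763. The documents give none of these tolerability rates, so the range is:

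| Tier-6 tolerability | Tiers 1–5 at 100% | at 98% | at 95% |
|---|---|---|---|
| 1/2 | 0.875 | 0.763 | 0.605 |
| 1/3 | 0.704 | 0.580 | 0.426 |

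**Reading B: significantly above 90% (null: 90% or less), exact binomial.**
- 24/24 gives p = 0.9^24 = 0.080. No result passes.
- The smallest size that can pass is 36, where 0.9^36 = 0.0225 and every patient must tolerate.
- 48/48 gives p = 0.9^48 = 0.0064; 47/48 gives p = 0.040. One failure in any tier blocks the claim for all six.

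**Reading C: not significantly below 90% (null: 90% or more).** The number of failures is Binomial(N, 0.1) at the boundary.
- N = 24: P(6 or more) = 0.028 and P(7 or more) = 0.0075, so up to 6 failures pass. All 3 active patients in tier 5 and all 3 in tier 6 could fail.
- N = 48: P(9 or more) = 0.046, so up to 9 failures pass.

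**What tier results could show (exact 95% intervals).** 1/3: 0.8% to 90.6%. 2/6: 4.3% to 77.7%. When all n tolerate, the lower limit is 0.025^(1/n): 29.2% for 3/3, 54.1% for 6/6 and 73.5% for 12/12.

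**The case against.** - **The p value.** A reader might infer that tDCS will be declared tolerable even when most tier-6 patients stop early. The documents do not support that as a flat statement. It can happen under readings A and C; under B, a usual meaning of such a test, it cannot. The pass probabilities above belong to reading A alone.
- **Sham.** A reader might also infer that tier pooling alone hides failure of most of tier 6. At 18 and 36 active patients it does not: removing sham makes 2 of 3 and 4 of 6 fail the cut. Pooling alone suffices at some intermediate sizes, such as 19/21, and elsewhere it still hides 1 of 3 or 3 of 6.
- **The hypothesis is pooled.** Hypothesis I-c speaks of tolerating tDCS without naming tiers, so the rule matches it. This is true, but the pooled answer still does not deliver the Impact paragraph's aim.
- **Dose is not ignored.** The technician form records whether an event shortened stimulation, symptoms are compared by tier, and the DSMB reviews all safety data after each tier (E.1). D.6.10.2 rests the decision on further development on all outcome measures, so the pooled verdict is not the sole gate. These points soften the concern. None of them sets a completion criterion or plans a table of completion by tier.
- **The scenarios are pessimistic.** E.3.3 expects only infrequent cutaneous effects, and 48 patients requires every tier to expand after a SICH. This is fair; the 24-patient case is the more relevant one.

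**Conclusion.** The concern holds in a limited form. E.3.3 gives one pooled answer, includes patients who receive no current, and plans no completion result by tier, so the lead tolerability analysis cannot identify tolerated regimens under any of the three readings. The direction and size of the problem depend on the unstated null hypothesis. Under A, 2 of 3 tier-6 failures can pass at 24 patients. Under C, up to 6 failures of any kind can pass. Under B, nothing can pass at 24, and at 48 a single failure denies the claim to all tiers. The failure counts rest on the design numbers; only the pass probabilities rest on assumed tolerability rates.

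A reader might go further and ask each tier to meet 90% by itself. The sample sizes do not support this. With 3 or 6 patients it means 3/3 or 6/6. At a true 95%, all six three-patient tiers would pass only 0.95^18 = 40% of the time, while a tier at 50% would pass 0.5^3 = 12.5% of the time.

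**What to change.** In E.3.3:
1. Restrict the lead tolerability analysis to active patients.
2. State the null hypothesis and test behind the one-sided 0.025. If reading B is meant, note that with active patients only it can be met solely by 36/36 (33/33 gives 0.9^33 = 0.031), and decide whether that is intended.
3. Report the number completing at least 75% of the stimulus period by tier (x of 3 or x of 6) and by one, two or three cycles pooled over current (6 to 12 active patients each), with exact 95% confidence intervals.
4. Label these results descriptive, with no 90% pass or fail rule per tier.
5. Keep the pooled active rate as an overall summary, and say that it does not by itself establish tolerability of any individual tier.

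The cost is a few sentences and one table from data already collected; dosing, escalation and sample size do not change. The downside is that tier intervals will be wide, so the trial can claim less about each regimen.

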The demographic and baseline clinical characteristics of the study population will be delineated with standard descriptive statistics. Categorical variables describing the clinical history, examination findings, and initial treatment will be summarized by

frequencies. Continuous variables such as vital signs, laboratory results, and time variables will be characterized by means, standard deviations, and 95% confidence intervals (CI). Ordinal and non-normally distributed variables (such as the NIHSS) will be characterized by medians and interquartile ranges. Baseline characteristics will be compared between the tDCS stimulation group with sham group to assess covariate balance. Wilcoxon Rank-Sum tests will be used for continuous or ordinal variables; Fisher's exact tests and chi-square tests will be used for grouped or nominal categorical variables.

E.2.3. Safety and Tolerability (Specific Aim 1)

E.2.3.1 Dose Escalation

The study Data and Safety Monitoring Board (DSMB) will meet at the completion of each dose tier, review all safety data, and determine whether the study will proceed to the next dose tier. DSMB deliberations will be guided by: 1) a formal stopping/escalation rule, based on the occurrence of the lead safety endpoint, symptomatic intracranial hemorrhage (SICH), and 2) The DSMB members' clinical judgement upon review of all other safety outcomes. The formal dose escalation rule uses SICH frequency to gate the occurrence and pace of escalation through the 6 dose tiers. If no SICH occurs in the 3 active patients at a dose tier, enrollment may escalate to the next dose tier. If one SICH occurs, 3 more active (and 1 more control) patient will be enrolled at that dose tier before escalation. If 2 SICHs occur at a dose tier, further study enrollment is held until detailed review by the DSMB (Fig 6). In addition, whenever the formal SICH criteria for dose escalation has been met, the DSMB will formally meet, review the SICH data and all other safety data, and advice regarding proceeding to the next tier, continuing at the current tier, or placing the study on hold.

E.2.3.2. Primary Safety Endpoint Analysis

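### The tolerability success rule names no null rate or test, so 22/24 to 24/24 may pass or fail, and it counts sham patients who receive no current

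*Combined protocol and SAP*

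**What the plan says.** Section E.3.3 (Tolerability Endpoint Analysis) defines its lead endpoint as completing the assigned stimulation "without early cessation due to cutaneous, neurologic, nociceptive or other adverse effects". It then says a patient will be "considered to have tolerated the procedure if at least 75% of the stimulus period was completed". The treatment counts as generally tolerable if, "among all enrolled patients, tolerated procedures are achieved in" at least 90% of patients, "assessed with a one-sided p value of 0.025". No null rate, test, critical count or power is given.

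Only the secondary tolerability endpoints (rate and severity of the items on the two tolerability forms) are to be "descriptively compared between active treatment and sham patients, and between higher and lower dose tiers".

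Hypothesis I-c in section A uses the same 90% and 75% figures. It concerns tolerating tDCS, and it adds that there must be no major stimulation-related pain, discomfort or skin change.

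Section E.2.1 takes the sample size from the 3+3 design alone, which "yields a sample size of at least 24 and potentially up to 48". Under E.2.3.1, one symptomatic haemorrhage (SICH) in a tier means that "3 more active (and 1 more control) patient will be enrolled at that dose tier before escalation". The section on dose tiers and randomization says sham patients wear the cap and electrodes, with "switches moved but without any delivered electrical stimulation".

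**The concern.** A p value needs a null hypothesis, and this rule has none. The natural candidate is 90%, the only rate stated, but at the planned minimum even a perfect result would then fail. Reading 90% as an observed cut-off gives the opposite verdict for the same data and leaves the p value without a role. A well-tolerated device would be expected to produce results such as 22, 23 or 24 of 24, and these are the ones left undecided.

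Separately, sham patients cannot show that current is tolerated, yet they are a quarter of the denominator.

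This is the only stated success rule for one of the three hypotheses of Specific Aim I. If it stays open, the reading could be chosen after the data are seen.

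**Working it through.** **Inputs.** From E.3.3: threshold 90%, one-sided 0.025, all enrolled patients. From E.2.1: six tiers, 3 active to 1 sham. From E.2.3.1: a tier expands by 3 active and 1 sham after one SICH.

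**The plan's own figure.** 6 × (3+1) = 24 and 6 × 2 × (3+1) = 48, as stated. If all six tiers complete, the possible totals are 24 + 4k, where k is the number of expanded tiers (0 to 6). The arms are 18 + 6 at N=24 and 36 + 12 at N=48.

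**Reading A: 90% is the null.** For a perfect result, exact p = 0.9^n, mid-p = half of that, and the score test uses z = (1 − 0.90)/√(0.09/n) without continuity correction.

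| N | Exact | Score | Mid-p |
|---|---|---|---|
| 24 | 0.080 | 0.051 | 0.040 |
| 28 | 0.052 | 0.039 | 0.026 |
| 32 | 0.034 | 0.030 | 0.017 |
| 36 | 0.0225 | 0.023 | 0.011 |
| 48 | 0.0064 | 0.0105 | 0.0032 |

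- At N=24 nothing passes. The exact one-sided 97.5% lower limit for 24/24 is 85.8%.
- A perfect result first passes at N=36 by the exact and score tests (three expanded tiers) and at N=32 by mid-p (two). Since tiers expand only after an SICH, the claim would become reachable only if haemorrhages occur.
- One failure at N=48: 47/48 fails by exact (0.040) and score (0.034) and passes by mid-p (0.023).
- Chance of passing at an assumed true rate of 98%, exact / mid-p: N=24, 0% / 0%; N=32, 0% / 52% (0.98^32); N=36, 48% / 48% (0.98^36); N=48, 38% (0.98^48) / 75% (47 or more of 48).

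**Reading B: 90% is an observed cut-off.** The bar is the smallest whole number at or above 0.9N: 22/24 (91.7%), 33/36, 44/48. Against a 90% null, 22/24 has exact p = 0.564. Readings A and B disagree for 22–24 of 24, 33–35 of 36, and 44–47 of 48 (44–46 by mid-p).

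**Reading C: fail only if significantly below 90%.** Then 18/24 (75%) passes, with lower-tail p = 0.028.

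**Sham in the denominator, under Reading B.** If every sham patient completes, the active patients needed equal the pooled bar minus the number of sham patients.

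- N=24: 22 − 6 = 16 of 18 (88.9%), against 17 of 18 for active patients alone.
- N=28: 26 − 7 = 19 of 21, the same as for active patients alone.
- N=48: 44 − 12 = 32 of 36 (88.9%), against 33 of 36.
- At every design total except 28 the bar falls by one active patient.

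The chance of passing is the binomial tail in the active arm. True rates are assumptions.

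| True active rate | N=24, active only | N=24, pooled | N=48, active only | N=48, pooled |
|---|---|---|---|---|
| 80% | 10% | 27% | 5% | 13% |
| 85% | 22% | 48% | 19% | 35% |
| 90% | 45% | 73% | 51% | 71% |
| 95% | 77% | 94% | 90% | 97% |
| 98% | 95.0% | 99.5% | 99.4% | 99.9% |

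If each sham patient completes with probability 95% (assumption) rather than with certainty, the pooled figures at a true 85% are 41% at N=24 and 26% at N=48.

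**Definitions of tolerating (a minor point).** A patient stopped for pain at 80% of the stimulation period fails the first sentence of E.3.3 and meets the 75% rule. A patient who completes with major pain meets the 75% rule but not Hypothesis I-c.

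**The case against.** The failure of 24/24 depends on a superiority null at 90%, which the plan never states. Under Readings B and C, 22/24 to 24/24 all pass. That is correct, but a third reading that passes 18/24 widens the ambiguity.

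E.3.3 expects only infrequent adverse effects, and at true rates of 95–98% pooling matters less. This stands for N=48 and for the 98% case. At N=24 and a true 95%, pooling still raises the pass chance from 77% to 94%, and the direction always favours success when sham patients all complete.

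The technician form has a column for shortened stimulation, and its items are compared by arm. That captures part of the information, but it is not an analysis of completion by arm, and the success rule stays pooled.

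The 75% sentence in E.3.3 can fairly be read as putting the sentence before it into operation. The extra condition in Hypothesis I-c would still be unmatched.

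Finally, the rule gates nothing: SICH is the primary endpoint, and D.6.10.2 rests later development on all outcomes. This limits the severity.

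**Conclusion.** The concern holds and should be fixed. E.3.3 cannot be applied as written: at the planned minimum, 22/24 to 24/24 succeed or fail according to an unstated choice, and with 90% as the null none of the exact, score or mid-p tests allows success. That part rests on taking 90% as the null, which the plan does not say. The absence of any null or test is plain from the text.

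Counting sham patients lowers the observed-rate bar by one active patient at every design total but N=28, so an active-arm rate of 88.9% can be reported as meeting a 90% standard. The size depends on the assumed true rate and on sham completion: 22% to 48% at a true 85% and N=24, much less at 98%. The consequence is an undetermined or diluted tolerability claim. Dose escalation and the primary safety analysis are not affected.

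**What to change.** In E.3.3:

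1. Take patients randomised to active tDCS as the denominator, and report sham completion separately. This alone is not enough: 18/18 against a 90% null gives exact p = 0.9^18 = 0.150.
2. In addition, choose one of two rules.
   - Drop the 0.025 test. Require an observed active-arm rate of at least 90% (17/18 at the minimum, 33/36 at the maximum), reported with its exact one-sided 97.5% lower limit (17/18: 72.7%; 18/18: 81.5%; 33/36: 77.5%).
   - Keep a test, name it, and state a null below 90% that 18 to 36 active patients can exclude. For illustration, an exact test against 70% needs 17/18 (p = 0.014) or 31/36 (p = 0.022); against 80% it needs 18/18 (p = 0.018) or 34/36 (p = 0.016).
3. Reconcile the early-cessation sentence, the 75% rule and the no-major-effects condition of Hypothesis I-c.

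**Cost.** The changes are to wording only. Because protocol and SAP are one document, they would need IRB approval like any other protocol change. Under the first option the claim becomes an estimate with a wide lower limit. The 17/18 rule passes 77%, 45% and 10% of the time at true rates of 95%, 90% and 80%; the 33/36 rule passes 90%, 51% and 5%.
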